9.5.6 Week 12/Early Termination

- Complete physical examination; includes neurological examination and weight
- 12-lead ECG (triplicate)
- Vital signs after resting for at least 5 minutes
- Resting TTE
- Hemodynamic stress echocardiography after 4 hour fast
- CPET after a 4-hour fast (water is allowed). CPET may be conducted at the Week 12 visit or anytime between Weeks 10 and 12. If CPET and hemodynamic stress echocardiography are conducted at the same visit, the hemodynamic stress echocardiography should be conducted first, followed by the CPET.
- Blood samples for
 - Hematology and serum chemistry
 - NT-proBNP
 - Potential exploratory biomarker analysis
 - PK (within ≤ 2 hours prior to dosing)
- Pregnancy test (blood or urine) for women of childbearing potential, based on standard at institution
- Urine sample for urinalysis
- Retrieve previously applied cardiac monitoring skin patch and apply a new patch. The skin patch is only required for up to 2 weeks of wear time.
- Optical biosensor pulse wave analysis (consenting subjects)
- Concomitant therapy assessment
- AE assessment
- Study medication compliance
- Dyspnea NRS
- KCCQ
- NYHA class
- Open-label MYK-461 administration at site

9.5.7 ***Week 16/End of Study***

- Complete physical examination; includes neurological examination and weight
- 12-lead ECG (triplicate)
- Vital signs after resting for at least 5 minutes
- Resting TTE
- Hemodynamic stress echocardiography after 4 hour fast
- Blood samples for
 - Hematology and serum chemistry
 - NT-proBNP
 - PK
- Urine sample for urinalysis
- Pregnancy test (blood or urine) for women of childbearing potential, based on standard at institution
- Retrieve cardiac monitoring skin patch
- Optical biosensor pulse wave analysis (consenting subjects)
- Concomitant therapy assessment
- AE assessment
- Dyspnea NRS
- KCCQ
- NYHA class

9.5.8 ***Unscheduled Visits***

At the investigator's discretion, unscheduled visits may be conducted for the assessment of AEs, physical examinations, vital signs, laboratory tests, ECGs, and/or TTEs. All information collected from unscheduled visits will be recorded on the eCRF and included in the clinical database.

9.6 **Visit Window and Missed Visits**

Weekly visits should occur within the visit window (\pm 1 day). If an evaluation is missed, reschedule and perform it as close as possible to the original date. If rescheduling becomes, in the investigator's opinion, medically unnecessary because the evaluation would occur too close to the next scheduled evaluation, it may be omitted.

10 EVALUATION, RECORDING, AND REPORTING OF ADVERSE EVENTS

10.1 Definitions

10.1.1 Adverse Event

An AE is any untoward medical occurrence, or the deterioration of a preexisting medical condition (other than the condition that is being treated by the study) associated with the use of a study medication in humans, whether or not it is considered related to the study medication. An AE (also referred to as an adverse experience) can therefore be any unfavorable and unintended sign (e.g., tachycardia, enlarged liver, clinically important abnormal laboratory result or diagnostic procedure), subject-reported symptom (e.g., nausea, chest pain), or evidence of any disease activity temporally associated with the use of a study medication, whether or not related to the study medication.

In clinical studies, an AE can include an undesirable medical condition occurring at any time after the subject has signed informed consent, including run-in or washout periods, even if no specific treatment has been administered.

Preexisting medical conditions (other than natural progression of the disease being studied) judged by the investigator or subject to have worsened in severity or frequency or changed in character during the protocol-specified AE reporting period will be reported as AEs or SAEs as appropriate.

Imaging-based assessments of decrease in contractility are not considered AEs unless associated with symptoms or signs of clinical concern on the part of the investigator. Such events should be categorized as an AE defined in terms of those symptoms or signs.

An AE or SAE can also be a complication that occurs as a result of protocol-mandated procedures (e.g., invasive procedures such as biopsies).

For MyoKardia to collect additional information about clinically important laboratory results or diagnostic tests (e.g., blood, ECG, imaging), at a minimum, the following abnormalities should be captured on the AE eCRF:

- Any test result that meets the definition of an SAE
- Any clinically important test abnormality that suggests a disease and/or organ toxicity that has worsened or is new (e.g., $>3\times$ deviation from the upper or lower limit of the analyzing laboratory reference range, or as otherwise specified in the protocol)
- Any test abnormality that required the subject to have study medication discontinued or interrupted or in the clinical judgment of the investigator.
- Any test abnormality that required the subject to receive specific corrective therapy, close observation, more frequent follow-up assessment, or further diagnostic investigation.

The term AE is used generally to include any AE whether serious or non-serious.

10.1.2 *Serious Adverse Event*

An SAE is an AE that fulfils one or more of the following criteria in the opinion of the investigator or MyoKardia:

- Results in death
- Is immediately life-threatening (places the subject at immediate risk of death from the event as it occurred)
- Requires in-subject hospitalization or prolongation of existing hospitalization
- Results in persistent or significant disability or incapacity or substantial disruption of the ability to conduct normal life functions
- Results in a congenital abnormality or birth defect
- Is an important medical event that may not result in death, be life-threatening, or require hospitalization, but may be considered an SAE when, based upon appropriate medical judgment, it may require medical or surgical intervention to prevent one of the outcomes listed above.

10.2 Adverse Event Reporting and Descriptions

10.2.1 *Reporting Period and Follow-Up*

AEs will be assessed from the time the subject provides informed consent through the duration of the study. Preexisting medical conditions that increase in severity from the first dose of study medication will be reported as AEs. Preexisting medical conditions that increase in severity after providing informed consent but before the first dose of study medication will be reported as medical history.

Any AEs that are unresolved at the subject's last visit in the study are followed by the investigator until resolved, or stabilized and are considered irreversible, or the subject has died.

MyoKardia retains the right to request additional information for any subject with ongoing AE(s)/SAE(s) at the end of the study, if judged necessary.

10.2.2 *Adverse Event Attributes*

The following attributes will be recorded for each AE. Additional attributes may be collected as required by MyoKardia

10.2.2.1 Description

All AEs spontaneously reported by the subject or reported in response to the open question from the study personnel: *“Have you had any health problems since you were last asked?”*, or revealed by observation will be collected and recorded in the eCRF.

When collecting AEs the recording of diagnoses is preferred (when possible) to recording a list of signs and symptoms (e.g., anemia, not low hemoglobin). However, if a diagnosis is known and there are other signs or symptoms that are not generally part of the diagnosis, the diagnosis and each sign or symptom will be recorded separately.

Death is an outcome and not the name of the event. In this situation, the event that led to the death is the name of the event. If the cause of death is unknown, “found dead” is an acceptable description.

10.2.2.2 Start Date/Time and Stop Date/Time

Record the date (and time during period of residency) the AE started and the date (and time during period of residency) the event ended. For events that continue for long periods of time, it is acceptable to record the end date as the day the event stabilized.

10.2.2.3 Relationship to Study Treatment (Suspected Adverse Reactions)

The investigator should assess causality by answering either “yes” or “no” to the following question, “is there a reasonable possibility that the event may have been caused by the IMP/study medication?”

10.2.2.4 Intensity

Record the intensity or severity of the event using the following guide:

- mild (awareness of sign or symptom, but easily tolerated)
- moderate (discomfort sufficient to cause interference with normal activities)
- severe (incapacitating, with inability to perform normal activities)
- life-threatening (urgent intervention indicated)
- fatal (event lead to death)

10.2.2.5 Seriousness

Record SAE criteria described in [Section 10.1.2](#) or indicate that the AE is not serious.

It is important to distinguish between category (AE vs SAE) and intensity (mild, moderate or severe) of AEs.

Severity is a measure of intensity (Section 10.2.2.4), whereas seriousness is defined by the criteria in Section 10.1.2.

An AE of severe intensity need not necessarily be considered serious. For example, nausea that persists for several hours may be considered severe nausea, but not an SAE. On the other hand, a stroke that results in only a limited degree of disability may be considered a mild stroke but would be an SAE.

10.2.2.6 Outcome

Record the outcome of the event based on the options provided on the eCRF.

10.3 Reporting and Evaluation of Serious Adverse Events

All SAEs regardless of causality will be reported by the investigator or designee to MyoKardia/designee through the last visit or 30-day period after the last dose of study medication, whichever is longer, within 24 hours of knowledge of the event or sequelae. Deaths and SAEs occurring beyond this timepoint and considered related to study medication or study procedure must also be reported. SAE reporting instructions are provided in the Study Reference Manual.

Suspected unexpected serious adverse reactions (SUSARs) are SAEs that qualify for mandatory expedited reporting to regulatory authorities where the SAE is suspected to be caused by the study treatment and is considered unexpected (i.e., not defined as expected in the current IB, clinical protocol, or approved labeling for marketed products). In this case, MyoKardia or designee will report to the relevant regulatory authority(ies) and forward a formal notification describing the SUSAR to investigators, according to regulatory requirement. Each investigator must then notify his/her ethics committee (EC) of the SUSAR as required by local regulatory authorities and in accordance with their EC policy.

11 STATISTICAL METHODS

11.1 Determination of Sample Size

Approximately 10 subjects will be dosed in Part A and in Part B. The sample size is based on practical considerations and is consistent with this type of study. Ten subjects per group receiving MYK-461 will provide 80% power to detect a 30 mm Hg within-group change from baseline in post-exercise peak LVOT gradient and a > 99% power to detect a 50 mm Hg change (Table 4). This assumes a 1-sided $\alpha = 0.05$ and a common standard deviation of 35 mm Hg. The common standard deviation of 35 mm Hg is based on observed data in patients with HCM and provokable LVOT (Nistri et al, 2012).

Table 4 **Power for Detecting a Statistically Significant Within Group Change With 10 Subjects^a**

Difference Versus Baseline In Peak LVOT Gradient (mm Hg)	Power (%)
50	> 99
40	95
30	80
20	50

LVOT, left ventricular outflow tract

^a Calculations were made using nQuery 7.0 Advisor software.

11.2 Study Endpoints

11.2.1 Primary Endpoint

- Change in post-exercise peak LVOT gradient from baseline to Week 12

11.2.2 Secondary Endpoints

- Proportion of subjects achieving an LVOT gradient response of post-exercise peak gradient < 30 mm Hg
- Change in dyspnea symptom score from baseline to Week 12
- Change in pVO₂ and VE/VCO₂ from baseline to Week 12
- Change from baseline in LVEF (2D and 3D), global longitudinal strain, and LVFS from baseline to Week 12
- Change from Week 12 to Week 16 in post-exercise peak LVOT gradient
- Plasma PK profile of MYK-461

11.2.3 Exploratory Endpoints

- Proportion of subjects achieving an LVOT gradient response of post-exercise peak gradient < 10 mm Hg
- Change in NYHA functional classification from baseline to Week 12
- Change in NT-proBNP from baseline to Week 12
- Change in KCCQ OSS from baseline to Week 12
- Change from baseline in arterial pulse wave morphology assessed using an optical biosensor

- Change from baseline in HR and heart rhythm assessed using a cardiac monitoring skin patch

11.2.4 Safety Endpoints

- Treatment-emergent AEs and SAEs
- Changes from baseline in laboratory values and vital signs
- Changes from baseline in ECGs

11.3 Statistical Analysis

Before database lock, a final statistical analysis plan (SAP) for clinical data and PK analyses will be prepared that will contain full details of all planned analyses. The analyses presented here represent an outline of the intended methodology.

11.3.1 Analysis Populations

Three analysis populations are defined in this study.

The Efficacy/PD Analysis Population is defined as all subjects who receive at least 1 dose of MYK-461 and have primary or secondary endpoint data, including a baseline value and at least one post baseline value. All efficacy and PD analyses will be performed on the Efficacy/PD Analysis Population.

The Safety Analysis Population is defined as all subjects who receive at least 1 dose of MYK-461. Safety analyses will be performed on the Safety Analysis population.

The PK Analysis Population is defined as all subjects who received at least 1 dose of MYK-461 and have detectable PK data. PK analyses will be performed on the PK Analysis Population.

11.3.2 General Considerations

Descriptive summary statistics for continuous variables will include the number of subjects, mean, standard deviation, median, minimum, and maximum. Categorical variables will be summarized using counts and percentages. Ninety-five percent confidence intervals will be presented, as appropriate.

The two groups from Part A and Part B, respectively, will be analyzed separately and not statistically compared with one another for effect sizes. They may be compared side-by-side with respect to demographic and baseline characteristics to evaluate whether they were drawn from the same overall population.

11.3.3 Subject Disposition

The number and percentage of subjects who complete and discontinue as well as reasons for early discontinuation will be presented.

11.3.4 Demographics and Baseline Characteristics

Demographic and baseline characteristics will be summarized descriptively.

11.3.5 Efficacy/Pharmacodynamic Analyses

All efficacy/PD analyses will be performed on the Efficacy/PD Analysis Population.

11.3.5.1 Primary Efficacy Endpoint

The primary efficacy endpoint is the change from baseline to Week 12 in post-exercise peak LVOT gradient.

Post-exercise peak LVOT gradient will be analyzed using a mixed-effect model with repeated measures (MMRM). All data available from baseline (Screening) to Week 16 (EOS) will be included and missing data will be accounted for by the MMRM model. The model will include the fixed categorical effects of timepoint: baseline, Week 4, Week 12 (end of treatment), and Week 16 (EOS).

This model will provide least-squares (LS) mean estimates with their corresponding standard errors at each time point. Comparison between baseline and Week 12 (end of treatment) will be based on the LS mean difference obtained from the MMRM, and will be presented with its associated 95% confidence interval. Statistical significance of the difference versus baseline will be evaluated at the 1-sided 0.05 level.

11.3.5.2 Secondary and Exploratory Efficacy Endpoints

The proportion of subjects achieving LVOT gradient responses of < 30 mm Hg and < 10 mm Hg will be summarized at each post-baseline visit. In case of missing data at a given visit, it will be assumed that the subject had not achieved an LVOT gradient response.

Quantitative endpoints, including the Dyspnea NRS, pVO₂, VE/CO₂, LVEF, NYHA functional classification, NT-proBNP, and KCCQ OSS will be analyzed using the same MMRM model as for the primary efficacy endpoint. The list of timepoints included in the MMRM will be adjusted according to the visits at which each endpoint will be measured.

Data collected from the optical biosensor and cardiac monitoring skin patch will be analyzed descriptively.

11.3.6 Pharmacokinetic Analyses

Plasma concentrations of MYK-461 will be determined and summarized descriptively. Population PK and PK/PD analyses will be conducted.

11.3.7 *Interim Analysis*

No formal interim analysis is planned.

11.3.8 *Safety Analyses*

All safety analyses will be performed on the Safety Analysis population.

11.3.8.1 Adverse Events

AEs will be mapped to system organ classes and preferred terms using the Medical Dictionary for Regulatory Activities (MedDRA). AEs will be monitored during the study and the data analyzed with respect to overall incidence as well as severity and potential relationship of AEs to study medication. AEs with onset on or after the first dose of study medication, or with an onset before the first dose of study medication that increase in severity on or after the first dose of study medication, will be considered treatment-emergent. Treatment-emergent AEs will be summarized for the Safety Analysis Population by system organ class and preferred term, and by severity and relationship to treatment. Severe and life-threatening AEs, SAEs, and AEs leading to study withdrawal, if any, will be presented in data listings.

11.3.8.2 12-lead Electrocardiogram

The RR, PR, QRS, and QT intervals will be measured. HR will be calculated as $60/(RR \times 1000)$ (with RR expressed in msec) and rounded to the nearest integer.

Correction for Heart Rate

Corrected QT interval (QTc) will be calculated using the manually over-read QT values. Each individual ECG QT value will be corrected for HR. The measured QT data will be corrected for HR using the Fridericia method (QTcF) as per the following formulae/method (with QT, RR and QTc expressed in msec):

Fridericia's Correction:

$$QT_{cF} = \frac{QT}{(RR / 1000)^{1/3}}$$

ECG Numeric Variables

HR, PR, QRS, and QTcF will be summarized using descriptive statistics. The change from baseline of these ECG parameters at each timepoint will be listed for each subject. For each timepoint of measurement, the changes from baseline will be summarized using descriptive statistics.

Categorical Analysis

The incidence count and percentage of subjects with any postdose QTcF values of > 450 msec, > 480 msec, and > 500 msec will be tabulated for all subjects. Subjects with QTc values > 500 msec will be listed with corresponding baseline values, Δ QTcF, and baseline and treatment HR. The incidence count and percentage of subjects with Δ QTcF increase of > 30 msec and > 60 msec will be tabulated.

Morphology Findings

New ECG morphologies for each subject not present on any ECG at baseline for that subject will be summarized for all observation timepoints combined.

The number and percentage of subjects having T-wave morphology changes and/or the occurrence of abnormal U-waves that represent the appearance or worsening of the morphological abnormality from baseline will be reported.

Concentration-QTc Analyses

A concentration-QTc regression analysis, based on data collected from the ECG recordings after drug administration and concentration values for each subject at each matching timepoint, will be performed.

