3.4. Dose Adjustment/Modifications

All subjects in Part A will be assigned to a starting dose of oral MYK-461 based on body weight for doses ≥ 10 mg, which they will receive QD for 4 weeks. Subjects in Part B will be assigned a starting dose of 2 mg. At the Week 4 visit, dose adjustment may be performed based on the predetermined criteria in Section 3.1, Table 1 (Part A) and Table 2 (Part B). The subject will subsequently receive that dose from Week 5 (Day 29) through Week 12.

Subjects with abnormal hepatic laboratory values (e.g., alkaline phosphatase [ALP], aspartate aminotransferase [AST], alanine aminotransferase [ALT], total bilirubin [TBL], or international normalized ratio) or signs/symptoms of hepatitis may meet the criteria for withholding of study medication or other protocol-required therapies. Withholding is either permanent or conditional depending on the clinical circumstances discussed in the protocol.

4. General Statistical Considerations

All statistical analyses and programming of tables, figures, and listings will be performed by PPD using the SAS® Version 9.2 or higher (SAS Institute Inc., Cary, North Carolina, USA).

Unless otherwise specified, all tables will be presented with the columns labeled with the combination of 'initial dose'/'adjusted dose'.

Descriptive summaries will consist of the number and percentage of subjects in each category for discrete variables, and the sample size, mean, median, standard deviation (STDEV), first and third quartiles, minimum and maximum for continuous variables. For the analysis of primary endpoint using a mixed-effect model with repeated measures (MMRM), LS mean with standard error (SE) will also be provided. Standard error formatting should be presented to 4 more decimal places than the measured value.

P-values will be rounded to 4 decimal places. P-values that round to 0.0000 will be presented as '< 0.0001' and p-values that round to 1.000 will be presented as '> 0.9999'. Confidence intervals (CIs) will be estimated based on the MMRM for the analysis of the primary endpoint, a two-sided 90% significance level.

All mean and quartile values will be formatted to one more decimal place than the measured value. Standard deviation values will be formatted to 2 more decimal places than the measured value. All percentages will be rounded to 1 decimal point. The number and percentage of responses will be presented in the form XX (XX.X), where the percentage is in the parentheses.

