9.5. Electrocardiogram

Triplicate ECG recordings will be obtained at each scheduled timepoint and the average of the three readings will be used to determine ECG intervals, including QRS, heart rate, PR, QT, Corrected QT interval using Fridericia's formula (QTcF), Corrected QT interval using Bazett's formula (QTcB) and RR. Missing ECG data will not be imputed. If one or two replicates are missing, the average will be calculated on the available replicates.

ECG Numeric Variables

HR, PR, QRS, QT, QTcF, QTcB, and RR will be summarized using descriptive statistics. The change from baseline of these ECG parameters at each timepoint will be listed for each subject. For each timepoint of measurement, the changes from baseline will be summarized using descriptive statistics.

Categorical Analysis

The cumulative incidence count and percentage of subjects with any postdose QTcF values of > 450 msec, > 480 msec, and > 500 msec will be tabulated for all subjects. Subjects will be listed with corresponding baseline values, Δ QTcF, and baseline and treatment HR. The cumulative incidence count and percentage of subjects with Δ QTcF increase of > 30 msec and > 60 msec will be tabulated. Also subjects with QTcB/QTcF >480 ms and/or change from baseline in QTcB/QTcF >60 ms will also be listed in a separate listing.

Morphology Findings

New ECG morphologies for each subject not present on any ECG at baseline for that subject will be summarized for all observation timepoints combined.

The number and percentage of subjects having new morphology changes from baseline will be reported, and summarized as QTc Prolongation, ST depression, ST elevation, T-waves biphasic, T-waves flat, T-wave inversion, or U-wave abnormality.

ECG overall interpretation by visit will be presented in a listing.

For the schedule of ECG test, please refer to Appendix 1.

10. Pharmacokinetics

Blood samples for plasma PK analysis of MYK-461 will be collected within 2 hours prior to dosing at the following timepoints: Day 1, Week 1, Week 2, Week 3, Week 4, Week 5, Week 6, Week 7, Week 8, Week12 and Week 16 or End of Study (End of Treatment + 4 Week) for Part A and Part B.

Concentrations that are BLQ will be treated as zero for descriptive statistics. All missing concentrations will be treated as missing for descriptive statistics.

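### The protocol's ECG heart-rate formula multiplies RR by 1000 instead of dividing, and four SAP ECG safety listings are titled for the Efficacy Set

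*Protocol*

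**What the plan says.** **Heart rate.** Protocol section 11.3.8.2 (12-lead Electrocardiogram) gives the derivation: "HR will be calculated as $60/(RR \times 1000)$ (with RR expressed in msec) and rounded to the nearest integer". The Fridericia formula in the same section, also with RR in msec, divides RR by 1000. Heart rate is then a reported variable: "HR, PR, QRS, and QTcF will be summarized using descriptive statistics". Its change from baseline is listed and summarised, and baseline and on-treatment heart rate are shown beside high QTc values.

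Protocol section 11.3 leaves full detail to the SAP: "The analyses presented here represent an outline of the intended methodology". SAP section 9.5 says that "the average of the three readings will be used to determine ECG intervals, including QRS, heart rate, PR, QT" and further parameters, and that "HR, PR, QRS, QT, QTcF, QTcB, and RR will be summarized using descriptive statistics". It contains no heart-rate formula and does not say whether heart rate is a laboratory reading or is derived from RR.

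**Listings.** Protocol section 11.3.8 and SAP section 9 (which contains 9.5 Electrocardiogram) assign every safety analysis to the Safety population. SAP section 9.5 also promises an outlier display: "Also subjects with QTcB/QTcF >480 ms and/or change from baseline in QTcB/QTcF >60 ms will also be listed in a separate listing". In the SAP's list of outputs, that display (Listings 16.2.12.2.A and B) and the general ECG listing (16.2.12.1.A and B) carry the title Efficacy Set. ECG Tables 14.3.5.1 to 14.3.5.4 carry the title Safety Set.

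**The concern.** The heart-rate expression cannot return beats per minute, and it contradicts the conversion used a few lines later. It is the only heart-rate derivation in either document, so a programmer must either code a wrong value or correct it silently, outside the plan. At stake are the ECG heart-rate summaries, their changes from baseline, and the heart rate shown beside QTcF to help interpret the rate correction.

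The listing titles break the plan's own population rule. Membership of the Efficacy population requires endpoint data that the Safety population does not, so a subject who was dosed and had an ECG could be absent from the subject-level ECG listings while still being counted in the ECG tables.

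**Working it through.** **1. Heart-rate formula.** The documents give no worked heart-rate value to reproduce, so the check evaluates the formula directly. The RR values are illustrative assumptions.

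- As written: HR = 60/(RR × 1000)
- Consistent with the Fridericia formula: HR = 60/(RR/1000) = 60,000/RR, with RR in msec

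| RR (msec) | As written, RR in msec | As written, RR in seconds | Rounded, either unit | 60,000/RR (bpm) |
|---|---|---|---|---|
| 600 | 0.0001 | 0.1 | 0 | 100 |
| 800 | 0.000075 | 0.075 | 0 | 75 |
| 1000 | 0.00006 | 0.06 | 0 | 60 |

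Ratio of written to correct, RR in msec: (RR/1000)/(RR × 1000) = 1/1,000,000, whatever RR is.

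Over a deliberately wide assumed range of 300 to 2000 msec, the written formula gives 0.0002 to 0.00003 (RR in msec) or 0.2 to 0.03 (RR in seconds). The correct values run from 200 down to 30 bpm. To reach the rounding threshold of 0.5, RR must be 60/(0.5 × 1000) = 0.12 in whichever unit is used. Even in seconds that means 60/0.12 = 500 bpm. A wrong unit label therefore does not explain the formula.

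QTcF is QT/(RR/1000)^(1/3). Heart rate does not enter it, so QTcF values and categories are unchanged.

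**2. Listing titles.** Counts from the SAP's list of outputs:

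| Listings | Content | Number (A and B) | Title |
|---|---|---|---|
| 16.2.8.1 to 16.2.8.4 | Adverse events | 8 | Safety Set |
| 16.2.9.1 to 16.2.9.3 | Laboratory | 6 | Safety Set |
| 16.2.10 | Vital signs | 2 | Safety Set |
| 16.2.11 | Physical examination | 2 | Safety Set |
| 16.2.12.1 and 16.2.12.2 | ECG | 4 | Efficacy Set |

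That is 8 + 6 + 2 + 2 = 18 titled Safety Set and 4 titled Efficacy Set, 22 in all.

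The two populations differ in two ways (SAP sections 4.3.2 and 4.3.3). Safety needs one dose; Efficacy also needs a baseline and a post-baseline value on a primary or secondary endpoint. Safety subjects are grouped by the dose combination actually received, Efficacy subjects by the planned one.

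**Who could be missing.** An ECG is taken 1 hour after the first dose (SAP Appendix 1, footnote g), so a subject can have postdose ECG data after a single day. Resting echocardiography and the Dyspnea NRS are scheduled at Weeks 1 to 8, 12 and 16, which makes 10 post-baseline site visits. A subject drops out of the four listings only if no usable endpoint value exists at any of these or at early termination.

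**What would be lost.** A QTcF outlier in such a subject would still be counted in Table 14.3.5.2 (Safety Set). For QTcB, the listing is the only display with a stated threshold. An extreme QTcB could still appear in the Safety Set summaries, which report "the sample size, mean, median, standard deviation (STDEV), first and third quartiles, minimum and maximum for continuous variables", or in the morphology table, where findings are "summarized as QTc Prolongation, ST depression, ST elevation, T-waves biphasic, T-waves flat, T-wave inversion, or U-wave abnormality". What is lost is the subject-level line, not necessarily the signal.

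**The case against.** The strongest reply is that neither slip is likely to reach a result.

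- **The formula may never be programmed.** The protocol calls its analyses an outline, ECG data go to a central cardiac laboratory (section 9.3.3), and Tables 14.3.5.1 and 14.3.5.4 carry labels, ERT and HBPRI, that look like data sources. Heart rate may simply be supplied. That is plausible but unproven: the protocol says heart rate is to be calculated, and the SAP does not settle it.
- **The intended conversion is obvious.** Moving one bracket, to (60/RR) × 1000, repairs the expression, and an all-zero column would be seen. This limits the harm but does not make the printed rule right. A fault in converting the PDF cannot be fully excluded either, although the expression is intact, its unit note is explicit and the Fridericia formula beside it is correct. The sponsor can check the source document.
- **The body text already fixes the population.** True, which is why the titles are wrong rather than merely ambiguous. Programmers commonly work from output titles, so the conflict should be removed.
- **There are backstops, and few subjects are exposed.** ECG findings the investigator judges clinically important become adverse events and appear in Safety Set listings, though without interval values. Plasma PK is itself a secondary endpoint, which makes exclusion from the Efficacy population rarer still. SAP section 9.5 also mentions listing subjects in the QTcF categories, but no separately named output exists for it. And the QTc Prolongation morphology category is undefined, so whether it applies a QTcB threshold is unknown.
- **These are two unrelated slips.** Correct; they share only the ECG safety reporting, and each should be judged on its own.

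All of this bears on consequence. The arithmetic and the titles stand.

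**Conclusion.** Both points hold, at minor severity. The heart-rate formula is wrong by a constant factor of 1,000,000 with RR in msec and rounds to 0 at any physiological RR in either unit. Its reach is confined to derived ECG heart rate. Four of the 22 safety-data listings, all of them ECG, name a population that contradicts the governing rule.

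The formula result depends on the printed expression only; the RR values used are illustrative. The effect of the listing titles depends on whether any dosed subject lacks an evaluable post-baseline endpoint value. The documents cannot show this, and with about 10 subjects per part the number may be 0. The primary endpoint, the sample size and the QTcF conclusions are not affected.

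**What to change.** 1. Protocol section 11.3.8.2: replace the expression with HR = 60/(RR/1000) = 60,000/RR, RR in msec, rounded to the nearest integer.
2. SAP section 9.5: add one sentence that either restates this formula or says that heart rate is the central-laboratory reading averaged over the triplicate.
3. SAP list of outputs: retitle Listings 16.2.12.1.A, 16.2.12.1.B, 16.2.12.2.A and 16.2.12.2.B from Efficacy Set to Safety Set.

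The cost is one formula, one sentence and four titles. Data collection, the QTcF analyses and the primary analysis do not change.
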